4.8 Ticks

Larval ticks will be obtained from [name] from a laboratory maintained tick colony at Tufts Veterinary School. These ticks are hatched from eggs laid by ticks that have fed only on specific pathogen free laboratory animals that were purchased from established vendors. Larval and nymphal ticks will be maintained on CB17 SCID mice, which are highly susceptible to many infections since they are immunodeficient. Mice that serve as hosts to tick colony material are screened monthly by blood smear and PCR for the main deer tick-transmitted agents.

B. burgdorferi, *Babesia microti*, and *Anaplasma phagocytophilum* (human pathogens known to be transmitted by *I. scapularis* ticks) are not transmitted transovarially (from mother to larvae). Deer tick virus, a flavivirus closely related to Powassan virus, has been linked to rare cases of human encephalitis ^{54,55}. Deer tick virus is inherited; however, its presence is readily detected in

a laboratory colony fed upon mice because all mice die with paresis within 4-14 days. There are some bacteria in ticks that can be transmitted transovarially including *B. miyamotoi*^{56,57}. There have been reports of *Bartonella spp.* in *Ixodes* ticks, but transmission of any *Bartonella* spp. by ticks to humans has not been established^{58,59}.

Each batch of ticks prepared for use in human xenodiagnosis will be tested for all known *Ixodes* transmitted human pathogens. Approximately one-third ($\frac{1}{3}$) of the larvae from each egg mass will be crushed and tested by PCR for the presence of the known human pathogens *B. burgdorferi*, *B. microti*, *A. phagocytophilum*, *B. miyamotoi*, *Bartonella* spp., deer tick virus and orbiviruses. In addition, a representative number of larvae from each batch (not less than 25) will be tested at [name] laboratory using a panel of broad-range primers targeting a wide range of genera including Spirochetes (all *Borrelia* species), *Francisella*, *Bartonella*, *Anaplasma*, *Ehrlichia*, *Rickettsia* and *Babesia*. Any egg mass that tests positive for any of these organisms (but for the *Rickettsia* endosymbiont of *I. scapularis*, see below) will be discarded. Production of additional ticks will be halted until a root-cause analysis of the source of the positive samples has been performed and the data presented to the Medical Monitor (MM) and the site PIs.

endosymbiont of *I. scapularis* (REIS, now known as *Rickettsia buchneri*)⁶³, there is no evidence of ill health resulting from the feeding of these ticks on study subjects. SCID mice have remained uniformly healthy after feeding ticks and we do not suspect any adventitious agent in our tick colonies that would compromise safety, regardless of the possibility of putative agents that have recently been or remain to be described. We will follow this general strategy as new agents that are not known human pathogens are identified. If a new pathogen is identified or a previously non-pathogenic organism is identified as a pathogen, use of ticks in xenodiagnosis will be halted until we develop a test to identify the presence of that pathogen or its products.

4.9 Testing of the Xenodiagnostic Ticks

Recovered larval ticks will be tested for the presence of *B. burgdorferi* by PCR, culture, and/or direct immunofluorescence. Other techniques with high sensitivity and specificity to detect *B. burgdorferi* and/or other tick-borne pathogens may be used as they become available.

4.10 Optional Skin Biopsy

Up to 4 optional skin biopsies will be collected to test for evidence of *B. burgdorferi* in the skin. The test results will be compared with the xenodiagnostic test results. Skin biopsies will be offered before the placement of ticks (either during Initial Visit or Tick Placement Visit) and after tick removal in patients with acute EM, untreated Lyme arthritis and PTLDS, and only after tick removal for participants in the Lyme disease, post-therapy group and for healthy volunteers. The reason for offering before and after placement for patients with acute EM, untreated Lyme arthritis and PTLDS is to be able to compare the results of the biopsy before and after and the results from the xenodiagnostic ticks, as tick feeding may increase the chance of finding *B. burgdorferi* in the skin site. Study results have shown that spirochetes were easily seen at the site of tick attachment after 4 days of feeding, but not on samples taken earlier⁶⁴. For participants in the Lyme disease, post-therapy group, recent unpublished data has shown that skin biopsies are negative in EM patients after 6 months of therapy. Therefore, only biopsies after tick removal will be done.

4.11 Discussion of Results

Participants will be informed that xenodiagnosis is an experimental test and therefore there are no guidelines to govern treatment of participants who test positive or negative by xenodiagnosis for the presence of *B. burgdorferi*. Participants will be notified of their test results by phone or in person at the completion of all testing of their ticks. The study doctor will discuss the implications of the test results with the subject.

5 RISKS

5.1 Xenodiagnosis

Anticipated risks to the participants include:

- 1) The development of allergic dermatitis from surgical tape used for sealing the mesh; or
- 2) The development of a mild or moderately pruritic or painful local reaction to the tick bite, which does not require medical attention.

From our experience with the 43 participants who underwent the xenodiagnosis procedure, the procedure is very well tolerated. All participants successfully completed the tick placement and

there were no withdrawals during the study. The most common AE was mild itching at the site, which was seen in 58% of participants, with a median duration of 3 days. Repeat of the xenodiagnosis procedure (performed in 7 participants), was similarly well tolerated with mild itching at the site being the most common complaint. There were no SAEs associated with the procedure. All these AEs resolved and did not require any intervention. No ticks escaped from the dressing.

Problems which may also occur and be serious but are not anticipated (and are therefore reportable as Unanticipated Adverse Device Effects [UADEs]) include:

- A) the development of a skin infection (cellulitis) from scratching or skin breaks secondary to 1 or 2 (above) or
- B) the remote possibility of developing tick paralysis
- C) the remote possibility of infection with a yet unknown pathogen
- D) the remote possibility of developing an allergy to red meat

Allergic dermatitis is typically self-limited with removal of the allergen (tape). Recovery may be aided by the application of topical steroids.

A minority of patients who have been bitten frequently by ticks will develop antibody responses to tick saliva and may develop a localized reaction with a granuloma. These reactions are self-limited.

Breaks in the skin caused by allergic dermatitis or scratching of tick bites can result in the development of cellulitis. Development of cellulitis secondary to allergic dermatitis or scratching is a very rare event, but could require either oral or intravenous antibiotic therapy.

Although the ticks are tested for all known human diseases that are transmitted by *I. scapularis*, the ticks are not sterile and do carry commensal organisms, and there is a possibility that a new, unknown pathogen may be carried by the ticks. If a new pathogen is identified or a previously non-pathogenic organism is identified as a pathogen, use of ticks in xenodiagnosis will be halted until we develop a test to identify the presence of that pathogen or its products.

Tick paralysis is a rare complication of tick bites. Patients present with acute symmetric ascending flaccid paralysis that generally begins in the lower extremities. Paralysis can ascend to the upper extremities, followed by cranial nerve involvement and respiratory muscle involvement, if the tick is not removed. Occasional patients may present with focal weakness or a cerebellar presentation. Removal of the tick is the definitive therapy, and patients will usually improve quickly after removal; however, symptoms can progress after tick removal (most commonly in Australian cases, associated with *I. holocyclus*). Most cases in North America are associated with the bites of *Dermacentor andersoni* (the wood tick) and *D. variabilis* (the dog tick), occur in children under the age of 10, particularly girls (probably because long hair make difficult to notice the feeding tick), and the tick is attached to the head or neck. *I. holocyclus* is the predominant species causing tick paralysis in Australia⁶⁵. *I. scapularis* is not associated with this disease, although a case associated with *I. scapularis* was reported in Mississippi⁶⁶. Assuming the tick identification was correct, it seems to be a highly unusual complication when

compared with the very high number of deer tick bites that occur yearly. A neurotoxin produced in the saliva of female ticks causes the paralysis. The *I. holocyclus* toxin has been identified and is named holocyclotoxin. The transcriptome analysis of over 8000 expressed sequence tags from 6 different salivary gland cDNA libraries from *I. scapularis* showed only a poor match with holocyclotoxin, suggesting the toxin is not found in *I. scapularis*⁶⁷. Therefore, it is highly unlikely that patients in this study will develop tick paralysis as a complication of tick placement, as *I. scapularis* is not associated with this disease, ticks being used are in the larval stage (adult female ticks are usually the stage associated with tick paralysis), and patients in the study are adults.

There has been an association between serious allergic reactions to red meat (including delayed anaphylaxis) and tick bites in some susceptible individuals^{68,69}. It is caused by an IgE antibody that binds to galactose- α -1,3-galactose (alpha-gal). Individuals with red meat allergy often reported a more severe local reaction to tick bites, with significant itching and redness around the bite. It is unknown if this allergy can develop after *I. scapularis* bites. The association has been described in Australia with *I. holocyclus*⁶⁸. It has also been described in patients in the southern US⁷⁰. A study suggested that as many as 20% of the population in Virginia, North Carolina, and Tennessee states, regions where *Amblyomma americanum* is common, have serum IgE antibodies to alpha-gal⁶⁹. Individuals in the southeastern US (where *Amblyomma* is more prevalent) are more likely to have antibodies against alpha-gal than individuals from Boston and Scandinavia⁶⁹. Patients with a history of severe reactions to tick bites are excluded from participation in the protocol, but it is possible that exposure to ticks may trigger a future allergic reaction in susceptible individuals. No reports of meat allergy were seen in the Phase I trial of Xenodiagnosis.

Anaphylaxis following a tick bite has rarely been reported^{71,72-74}. These reports include the *Argus reflexus*, *Rhipicephalus sanguineus*, *I. holocyclus* and *I. ricinus*. However, to our knowledge, it has not been reported in *I. scapularis* ticks. Recurrent anaphylaxis has been reported in *I. pacificus*, a tick that is closely related to *I. scapularis*⁷⁵. Allergic reactions may follow the bite of any of the different tick life cycle forms and is related to the release of salivary protein. Because these reactions are rare, it is uncertain whether repeated tick bites increase the risk of anaphylaxis.

Repeat of the xenodiagnosis procedure may increase the risk of sensitization and local reactions. It is known that people can become sensitized to tick bites over time and after having had many tick bites. A study of *I. scapularis* bite reactions and their protective effect against acquisition of Lyme disease on Block Island, Rhode Island, showed that among 610 participants, 52% reported at least 1 tick bite (mean 2.2, 95% CI 2.0–2.4), and 32% reported itch with any tick bite. None reported anaphylaxis associated with tick bite. The probability of itch doubled as the number of reported tick bites increased from 1 to 2 (21% to 46%, respectively) and doubled again from 2 to 4 reported bites (46% to 97%, respectively; linear trend $p < 0.001$). There was an inverse relationship between tick itch reaction and development of Lyme disease. The likelihood of Lyme disease infection decreased with >3 reports of tick-associated itch (odds ratio 0.14, 95% CI 0.94–0.03, $p = 0.01$). The possible mechanisms include a heightened awareness by a person of an attached tick with removal of the potentially infecting tick before pathogen transmission can occur, premature detachment of ticks before pathogen transmission can occur, or neutralization

of some components of tick saliva that ensure successful feeding and facilitate pathogen transmission.^{76,77}

There is a risk that ticks, either fed or unfed, may escape from the dressing. Loss of ticks should not pose a risk to either the subject or other people in contact with the subject. *Ixodes* ticks require high moisture content and would not survive in an indoor or urban setting for more than 1 or 2 days. Unfed ticks would be uninfected and at most, would attach at a site other than the forearm on the subject or, possibly, on a family member. Fed ticks are not expected to feed again for 3-6 months. Because the ticks are tested and carry no known disease, an unfed tick that escaped into a suitable environment in the subject's yard or surrounding area, would not pose a threat to other humans, wildlife or add a new species into the environment. *Ixodes* ticks are highly prevalent in rural and suburban Massachusetts, Rhode Island, Connecticut, New York, Maryland, and Virginia.

5.2 Blood Drawing

The two hazards associated with blood drawing are those of venipuncture and those associated with blood loss. Risks of venipuncture are pain at the site of the needle stick, the potential formation of hematoma at the site of the needle stick, and a small potential for infection and/or inflammation at the site of the needle stick. Occasionally, individuals may faint as a result of vasovagal reactions to the procedure. The major risk of repeated blood drawing is anemia. Current guidelines for maximum amount of blood drawn for research will be followed.

5.3 Punch Skin Biopsy

Punch biopsies have a low incidence of infection, bleeding, non-healing, or significant scarring^{78,60}. Rarely, there may be injuries or damage to the structures beneath the skin site (such as an artery or a nerve). Patients rarely may have local allergic reactions to the tape. Severe allergic reactions (anaphylaxis) to lidocaine are very rare.

6 BENEFITS

There are no direct benefits to the study participants. If the xenodiagnostic test is positive, they will know that they still harbor *B. burgdorferi* in their body. It is currently unknown whether treatment with more or different antibiotics will be beneficial to these patients

The benefit to society is that if it is shown that patients continue to harbor bacteria after antibiotic therapy, this may result in a paradigm shift that will lead to new controlled therapeutic trials. In addition, xenodiagnosis may become a new method for diagnosing persistent infection after antibiotic therapy.

7 STUDY ANALYSIS

7.1 Sample Size Justification

This study is powered to detect difference in the positivity rate between symptomatic and asymptomatic individuals. Self-reported symptoms will be characterized using symptom scales, the SF-36v2 questionnaire and fatigue scales. We will use a composite score derived from the measurement to assign symptomatic and asymptomatic status to the participants.⁷⁹

While the majority of the patients with Lyme disease who were treated with antibiotic therapy were negative by xenodiagnosis in our Phase 1 study, the number of patients tested in each group was small and the upper limit of the 95% confidence interval of each proportion is relatively high (up to 46%). Also, an important caveat is that the number of tested xenodiagnostic ticks per participant in general was also small, and the number of engorged ticks that are tested for each individual is an important variable, as the more engorged ticks tested, the larger the probability of detecting a positive. For example, if the true sensitivity for a single engorged tick to detect the bacteria is 1/10 (based on results of the mice studies), then one would need to recover 14 engorged ticks to have 75% sensitivity and 22 fed ticks to have 90% sensitivity.

Based in our very preliminary data, the upper limit of the exact 95% confidence interval for the proportion of positive xenodiagnosis in symptomatic patients (10%) was 0.445. Table 2 shows the sample size needed for 80% power, with a Type I error rate of 0.05, assuming varying assumptions for the true prevalence rates for asymptomatics (p_1) and symptomatics (p_2). For example, with a total sample size of 86 individuals, there would be 80% power to detect a between-group difference in the positivity rate if the true prevalence is 5% or less in the non-symptomatics and at least 30% in the symptomatics, assuming equal numbers between the 2 groups, (43 non-symptomatics and 43 symptomatics).

Table 2: Sample Size Needed for 80% Power with a Type I Error Rate of 0.05, and Varying Assumptions for the True Prevalence Rates for Asymptomatics (p_1) and Symptomatics (p_2)

	$p_2 = 0.40$	$p_2 = 0.30$
$p_1 = 0.05$	54	86
$p_1 = 0.025$	46	68
$p_1 = 0.01$	42	60
$p_1 = 0$	40	56

Assuming a 10 to 20% rate of missing data due to failed screenings, assays or participant drop-out, we plan to recruit up to 100 individuals.

For the other groups post-Lyme disease syndromes (PLDS), acute EM, and untreated Lyme arthritis, the precision with which the rates can be estimated from the observed data depends on the true underlying response rate and the sample size. Exact Clopper-Pearson 2-sided 95% CIs for the observed positivity rate the different proposed group sizes and a range of numbers of positive individuals are shown in Table 3. Healthy volunteers (negative controls) results will be used for specificity of the testing.

Table 3: Exact 95% Confidence Interval for the Observed Positivity Rate, for Varying Group Size (N) and Observed Numbers of Positive Individuals

# of observed positives samples	N=20	N=40
0	(0.000, 0.161)	(0.000, 0.09)
1	(0.009, 0.236)	(0.004, 0.13)

2	(0.0279, 0.301)	(0.014, 0.165)
5	(0.112, 0.468)	(0.054, 0.261)
10	(0.299, 0.701)	(0.142, 0.402)
15	(0.531, 0.888)	(0.242, 0.529)
20	(0.838, 1)	(0.352, 0.648)

Data will be collected for any positive tests by xenodiagnosis. Because there is no gold standard test among those we will employ, comparative positivity rates between the tests will be determined. Summaries of patient characteristics will be assessed by study group. For categorical variables, the numbers and proportions will be tabulated; for continuous variables, the mean, median, SD, and interquartile range will be reported. Fisher's exact test will be used to examine the association of 2 categorical variables. For continuous variables, t-tests and nonparametric methods, such as the Wilcoxon or Spearman's correlation coefficient, may be used to assess associations between subgroups of patients.

AEs related to xenodiagnosis will be tabulated and summaries with numbers and proportions will be given.

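### Recruiting up to 100 keeps the 86 evaluable of Section 7.1's worked example only for losses up to 14%, not across the plan's own 10–20% range

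*Combined protocol and SAP*

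**What the plan says.** All of this is in Section 7.1, Sample Size Justification, unless another section is named.

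- "Table 2 shows the sample size needed for 80% power, with a Type I error rate of 0.05", for eight combinations of positivity in asymptomatic and symptomatic participants. The totals run from 40 to 86.
- One cell is worked through in the text: "For example, with a total sample size of 86 individuals, there would be 80% power". Its rates are 5% without symptoms against 30% with them, and it takes the two groups as equal in size, at 43 each.
- The recruitment figure follows Table 2 directly: "Assuming a 10 to 20% rate of missing data due to failed screenings, assays or participant drop-out, we plan to recruit up to 100". The plan does not say which cell or which loss rate gave 100.
- For the other groups the plan offers precision, not power: "Exact Clopper-Pearson 2-sided 95% CIs for the observed positivity rate the different proposed group sizes", shown in Table 3 at N=20 and N=40.
- Section 3.2 gives the enrolment sizes as 100, 40, 40, 40 and 20. They add up to the ceiling of 240 in Section 3.1, so there is no reserve.
- Section 7.1 names Fisher's exact test for the association of two categorical variables.

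**The concern.** A recruitment figure that follows a stated loss range should hold at the upper end of that range, or the text should say where it stops holding. Here the reader is given a size (86), a loss (10–20%) and a ceiling (100), and will assume that they fit together. If they do not, the 80% power in the worked example is not delivered over part of the plan's own assumption, and the ceiling leaves no room to make up the difference. A related question is whether Table 3, set at full enrolment, shows the other groups as more precisely estimated than they would be after the same loss.

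**Working it through.** **1. Reproduce Table 2.** Inputs from Section 7.1: p1 = 0.05, p2 = 0.30, alpha 0.05, power 80%, equal groups. Sidedness is not stated; two-sided is assumed because it reproduces the table. With d = p2 − p1 and p̄ = (p1 + p2)/2, the uncorrected size per group is

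m = [1.96·√(2p̄(1−p̄)) + 0.8416·√(p1(1−p1) + p2(1−p2))]² / d² = [1.96 × 0.5374 + 0.8416 × 0.5074]² / 0.0625 = 35.06.

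The continuity-corrected size is n = (m/4)·[1 + √(1 + 4/(m·d))]² = 42.7, rounded up to 43 per group, or 86 in total. The same formula gives all eight cells exactly (54, 86, 46, 68, 42, 60, 40, 56).

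**2. Apply the stated loss.** Recruits needed = evaluable / (1 − loss).

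| Table 2 total | at 10% loss | at 20% loss | within 100? |
|---|---|---|---|
| 86 | 86/0.90 → 96 | 86/0.80 = 107.5 → 108 | only to 14% |
| 68 (next largest) | 68/0.90 → 76 | 68/0.80 = 85 | yes |

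The break-even loss is 1 − 86/100 = 14%. At 20% loss, 100 × 0.80 = 80 remain, 6 short of 86. The other six cells are smaller than 68, so they are covered too. Only the 86 cell leads to a figure near 100, so it is the likely basis, though the plan does not say so.

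**3. Power at 80 evaluable, 5% v 30%.** To invert the continuity correction, use m = n(1 − 1/(n·d))² and z = (d√m − 1.96 × 0.5374)/0.5074.

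- n = 43: m = 35.37, z = 0.855, power 80.4%.
- n = 40: m = 32.40, z = 0.729, power 76.7%.

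Exact two-sided Fisher power, by enumerating all outcomes, is 84.4% at 43:43 and 82.1% at 40:40. The smallest equal-group total with at least 80% is 78.

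**4. Unequal groups.** The equal split is an assumption in Section 7.1. Section 1 puts persistent symptoms at 10–40% of treated erythema migrans patients at 12 months. With 80 evaluable, Fisher power (non-symptomatic:symptomatic) is:

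| Split | Symptomatic | Power |
|---|---|---|
| 40:40 | 50% | 82.1% |
| 48:32 | 40% | 82.8% |
| 60:20 | 25% | 78.3% |
| 64:16 | 20% | 72.8% |

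**5. Table 3.** If 10–20% were also lost in these groups, 40 becomes 36–32 and 20 becomes 18–16. The exact upper limit for 0 positives is 1 − 0.025^(1/n):

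| n | 40 | 36 | 32 | 20 | 18 | 16 |
|---|---|---|---|---|---|---|
| upper limit | 8.8% | 9.7% | 10.9% | 16.8% | 18.5% | 20.6% |

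The printed limit for 0/20 is 0.161, not 0.168. For 1/20 the printed lower limit is 0.009, where Clopper-Pearson gives 0.001 and Wilson 0.009. All 14 printed intervals agree with Wilson score limits to within 0.003.

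**The case against.** The strongest reply has three parts.

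First, 86 is offered as an example and is the most demanding of eight cells; no cell is named as the target. This stands. A reader might infer that Section 7.1 requires 86 and that 100 is simply too few. The text sets no such minimum, and 100 suffices for seven scenarios throughout and for the eighth up to 14% loss.

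Second, the continuity-corrected formula is conservative, and the named Fisher test keeps more than 80% power at 80 evaluable. This stands for equal groups. A reader might infer that the trial is underpowered at 20% loss; the shortfall of six does not by itself show that. But the reassurance depends on the assumed split. At 60:20 or 64:16 Fisher power is below 80%, and this can matter more than the six lost participants.

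Third, Table 3 is a conditional look-up by group size, and the loss assumption is attached only to the 100-person cohort. This also stands. A reader might infer that the plan overstates the precision of the other groups, but applying 10–20% to them is an inference. The plan gives no loss rate for them, and none that rules loss out.

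What remains is that the loss range and the ceiling do not agree for the one scenario the plan works through, and that Table 3's label does not match its numbers.

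**Conclusion.** The point holds in a limited form. For 5% v 30%, a ceiling of 100 delivers 86 evaluable only up to 14% loss; from there to 20%, more than half of the stated range, it does not. At the worst end, power falls by 3.7 percentage points on the plan's own formula (80.4% to 76.7%) and by 2.3 under Fisher at equal groups (84.4% to 82.1%). This rests on a two-sided 5% test and on loss that falls equally on both groups. The documents do not support a call for more patients. The Table 3 effect is smaller and conditional: about 1–2 points on the upper limit at N=40 and 2–4 at N=20, if the same loss applies. The mismatch between Table 3's label and its method does not depend on any loss assumption.

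**What to change.** Restate the recruitment sentence in Section 7.1 along these lines, with enrolment unchanged:

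> Recruiting 100 covers up to 14% loss for 86 evaluable. At 20% loss, 80 are evaluable; for 5% v 30%, power is then about 77% by the formula used for Table 2 and 82% by Fisher's exact test at 40:40, falling to 78% at 60:20 and 73% at 64:16 (non-symptomatic:symptomatic).

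Say which Table 2 scenario and which loss rate the 100 rests on.

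For Table 3, recompute the limits by the Clopper-Pearson method that its label names, and state whether the 10–20% loss applies to these groups. If it does, add columns at the evaluable sizes (32–36 and 16–18).

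The cost is a few sentences and one recomputed table. Some stated figures become slightly less favourable.

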Participants who underwent xenodiagnosis included 10 patients with high C6 antibody levels, 10 patients with post-treatment Lyme disease syndrome (PTLDS), 5 patients with acute erythema migrans after completion of antibiotic therapy, one patient with erythema migrans on therapy (who also underwent xenodiagnosis after antibiotic therapy), and 10 healthy volunteers. Seven patients underwent more than one xenodiagnosis procedure.

As no previous protocol for xenodiagnosis with *I. scapularis* larva in humans existed, we developed a retention dressing using the LeFlap™ (Monarch Labs, Irvine, CA) dressing, which was modified for use with ticks. Participants enrolled early in the trial had fewer ticks feed successfully due to issues with the tick retention dressing that resulted in entrapment of the ticks in the adhesive.

After modifying the dressing by adding a foam ring to create a barrier between ticks and adhesive, we were more consistently able to get between 30 and 50% of ticks to feed successfully.

Xenodiagnosis was well tolerated. All participants successfully completed the tick placement and there were no withdrawals during the study. The most common AE was mild itching at the site, which was seen in 58% of participants, with a median duration of 3 days. Repeat of the xenodiagnosis procedure was similarly well tolerated, with mild itching at the site as the most common complaint. There were no serious AEs associated with the procedure. Although not a primary goal of this pilot study, we did find 2 participants that tested positive and 2 participants who tested indeterminate for the presence of *B. burgdorferi* in the xenodiagnostic ticks.

In this Phase 2 study, we plan to expand our study of xenodiagnosis for Lyme disease in humans. Xenodiagnostic evidence that *B. burgdorferi* survives in humans after antibiotic therapy may fundamentally change the approach to patients with persistent symptoms and provide physicians and researchers with a new tool with which to study the mechanisms of disease.

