3.2 Inclusion Criteria

Criteria for the diagnosis and therapy for Lyme disease can be found at “The clinical assessment, treatment, and prevention of Lyme disease, human granulocytic anaplasmosis, and babesiosis: clinical practice guidelines by the Infectious Diseases Society of America”⁵.

Patients with Lyme disease, post-therapy (N=100)

1. Age 18 or older.
2. Lyme disease diagnosed in the previous 13 months, fulfilling the case definition of confirmed or probable Lyme disease by the US Centers for Disease Control and Prevention (CDC) <https://www.cdc.gov/nndss/conditions/lyme-disease/case-definition/2017/>.
3. Completion of 1 course of antibiotics at least 3 months and up to 12 months between the end of the therapy and the xenodiagnostic procedure.
4. Antibiotic treatment fulfills the Infectious Diseases Society of America guidelines for the recommended therapy for Lyme disease⁵.

Patients with post-Lyme disease complaints at least 12 months from initial treatment (N=40)

1. Age 18 or older.
2. Diagnosed with confirmed or probable Lyme disease fulfilling the case definition of Lyme disease by the CDC <https://www.cdc.gov/nndss/conditions/lyme-disease/case-definition/2017/>.
3. Received recommended antibiotic therapy for Lyme disease⁵ at least 12 months between the end of the initial antibiotic therapy and the xenodiagnostic procedure.
4. Persistent or recurrent symptoms that began or worsened within 6 months of the diagnosis and treatment for Lyme disease.

Acute EM (N=40)

1. Age 18 or older.
2. EM diagnosed by the study physician.
3. Receiving antibiotic therapy for Lyme disease for less than 48 hours.

Lyme Arthritis (N=40)

1. Age 18 or older.
2. Lyme arthritis⁵⁰ and have not received antibiotic therapy for the disease.

Healthy volunteers (N=20)

1. Age 18 or older.
2. No prior history of Lyme disease.
3. Negative whole cell enzyme-linked immunosorbent assay (ELISA) or C6-based antibody test for Lyme disease.

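### Table 3 is labelled exact Clopper-Pearson, but 13 of its 14 intervals are narrower Wilson score intervals

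*Combined protocol and SAP*

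**What the plan says.** Section 7.1 (Sample Size Justification) bases the power calculation on the comparison of symptomatic with asymptomatic patients (Table 2). For the PLDS, acute EM and untreated Lyme arthritis groups it offers precision instead, and says that Table 3 gives "Exact Clopper-Pearson 2-sided 95% CIs for the observed positivity rate". The caption says the same: "Table 3: Exact 95% Confidence Interval for the Observed Positivity Rate". The table covers 0, 1, 2, 5, 10, 15 and 20 positives with N=20 and N=40, which makes 14 cells.

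Section 3.2 plans 40 participants in each of those three groups and 20 healthy volunteers. Section 7.1 says of the healthy volunteers that their "results will be used for specificity of the testing".

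Earlier in the same section, the Phase 1 data are summarised with another exact limit: "the upper limit of the exact 95% confidence interval for the proportion of positive xenodiagnosis in symptomatic patients (10%) was 0.445". Section 1 gives 10 patients with PTLDS in Phase 1, so 10% is 1 of 10.

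No other interval method for a proportion is named anywhere in the document.

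**The concern.** The printed intervals are too narrow to be Clopper-Pearson intervals. That method inverts two one-sided exact binomial tests and is conservative, so at these sample sizes it is visibly wider than score-based intervals.

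Two things are at stake. First, Table 3 is the only statement of precision for the three groups of 40, which make up 120 of up to 240 participants. Its N=20 column also matches the healthy-volunteer group that will supply specificity; the document does not state that link, and it is inferred here from the matching size. Second, anyone who applies the method named in the text will report wider intervals than the protocol promised. The analysis text after Table 3 names no interval method for reporting, so the choice between the two could be made after the data are seen.

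**Working it through.** **Inputs.** Counts x = 0, 1, 2, 5, 10, 15, 20 and sizes n = 20, 40, with the printed limits, from Table 3. The method (exact, two-sided, 95%) is from the text and caption of section 7.1.

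**Formulas.**
- Clopper-Pearson: lower = 0.025 quantile of Beta(x, n − x + 1); upper = 0.975 quantile of Beta(x + 1, n − x); 0 when x = 0 and 1 when x = n.
- Wilson without continuity correction, with p = x/n and z = 1.96: [p + z²/(2n) ± z·√(p(1 − p)/n + z²/(4n²))] / (1 + z²/n).

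**One cell by hand, 0 of 20.** Both formulas have a closed form here. Exact upper limit: 1 − 0.025^(1/20) = 0.1684. Wilson upper limit: z²/(n + z²) = 3.8415/23.8415 = 0.1611. The table prints 0.161.

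**All cells.** The last column is exact width divided by printed width, minus 1.

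| x/n | Printed | Wilson | Clopper-Pearson | Exact wider by |
|---|---|---|---|---|
| 0/20 | 0.000, 0.161 | 0.0000, 0.1611 | 0.0000, 0.1684 | 5% |
| 1/20 | 0.009, 0.236 | 0.0089, 0.2361 | 0.0013, 0.2487 | 9% |
| 2/20 | 0.0279, 0.301 | 0.0279, 0.3010 | 0.0123, 0.3170 | 12% |
| 5/20 | 0.112, 0.468 | 0.1119, 0.4687 | 0.0866, 0.4910 | 14% |
| 10/20 | 0.299, 0.701 | 0.2993, 0.7007 | 0.2720, 0.7280 | 13% |
| 15/20 | 0.531, 0.888 | 0.5313, 0.8881 | 0.5090, 0.9134 | 13% |
| 20/20 | 0.838, 1 | 0.8389, 1.0000 | 0.8316, 1.0000 | 4% |
| 0/40 | 0.000, 0.09 | 0.0000, 0.0876 | 0.0000, 0.0881 | not wider |
| 1/40 | 0.004, 0.13 | 0.0044, 0.1288 | 0.0006, 0.1316 | 4% |
| 2/40 | 0.014, 0.165 | 0.0138, 0.1650 | 0.0061, 0.1692 | 8% |
| 5/40 | 0.054, 0.261 | 0.0546, 0.2611 | 0.0419, 0.2680 | 9% |
| 10/40 | 0.142, 0.402 | 0.1419, 0.4019 | 0.1269, 0.4120 | 10% |
| 15/40 | 0.242, 0.529 | 0.2422, 0.5297 | 0.2273, 0.5420 | 10% |
| 20/40 | 0.352, 0.648 | 0.3520, 0.6480 | 0.3380, 0.6620 | 9% |

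**Reading the table.** Of 28 limits, three are fixed at 0 or 1, which leaves 25.
- For 23 of them the distance from printed to Wilson is at most 0.0009, and from printed to exact 0.0034 to 0.0270.
- The other two, the upper limits at 0/40 and 1/40, are printed to two decimals, and both methods round to the printed figure. The lower limit at 1/40 still separates the methods: printed 0.004, Wilson 0.0044, exact 0.0006.
- Four limits equal Wilson by truncation rather than rounding: 0.468, 0.838, 0.054 and 0.529. The table shows two of these itself. The 20/20 lower limit should mirror the 0/20 upper limit (1 − 0.161 = 0.839, printed 0.838). The 5/20 upper limit should mirror the 15/20 lower limit (1 − 0.531 = 0.469, printed 0.468).

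**Other candidates.** Wilson with continuity correction, Agresti-Coull, Jeffreys, Wald, mid-P, Blaker and 90% Clopper-Pearson were also tried. None reproduces more than 2 of the 14 cells. Agresti-Coull reproduces two, 10/20 and 20/40, where it coincides with Wilson.

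**Cross-check within section 7.1.** For 1 of 10, the Clopper-Pearson upper limit is 0.4450 and Wilson is 0.4042. The section prints 0.445, so the exact method was used there and not in Table 3. The section's other Phase 1 figure, an upper limit of up to 46%, would fit exact 0/6 (0.459; Wilson 0.390). That reading assumes the figure refers to the 5 + 1 erythema migrans patients of section 1 and that none of them was positive after therapy. The document states neither, and it does not call that interval exact, so nothing here rests on it.

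**The case against.** The strongest reply is that the error has little practical weight. Table 3 illustrates planning with hypothetical counts. The study is powered on Table 2, and no sample size, threshold or stopping rule is tied to Table 3. Final intervals will be computed from observed data, so the printed cells will not carry into the results.

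At low counts, the likeliest after Phase 1, the upper limits barely move: 0.161 to 0.168 at 0/20, 0.13 to 0.132 at 1/40, 0.165 to 0.169 at 2/40, and no visible change at 0/40. The largest shift, 0.027, is at 10/20, an implausible count for healthy volunteers; in the N=40 column the largest is about 0.015. The text also introduces Table 3 for the three patient groups, and does not promise an interval around specificity.

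All of this stands, and it limits the importance of the point. It does not rescue the label. The printed values are legible and follow one other method throughout, so poor text extraction cannot explain them, and nothing elsewhere in the document corrects them. The lower limits at low counts also move by more in relative terms: at 2/40 the exact value is 0.006 against 0.014 printed.

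**Conclusion.** The concern holds. Thirteen of the 14 cells in Table 3 are not the intervals that the text and caption name. They are Wilson score intervals, and each is narrower than the exact one: exact widths are 4% to 14% greater for N=20 and 4% to 10% greater for N=40. The 0/40 cell is uninformative.

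If the N=20 column is meant for healthy volunteers and none of 20 is positive, the exact lower bound for specificity is 1 − 0.168 = 83.2%, against 1 − 0.161 = 83.9% from the table. That example rests on the inferred link between the column and the group. The main finding rests only on the printed limits and the stated method.

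This should be corrected before analysis. It misstates the only precision given for the three groups of 40, but it leaves Table 2, the powered comparison and every group size unchanged.

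**What to change.** Replace Table 3 with Clopper-Pearson values, which agree with the text, the caption and the 0.445 in the same section:

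| Positives | N=20 | N=40 |
|---|---|---|
| 0 | (0.000, 0.168) | (0.000, 0.088) |
| 1 | (0.001, 0.249) | (0.001, 0.132) |
| 2 | (0.012, 0.317) | (0.006, 0.169) |
| 5 | (0.087, 0.491) | (0.042, 0.268) |
| 10 | (0.272, 0.728) | (0.127, 0.412) |
| 15 | (0.509, 0.913) | (0.227, 0.542) |
| 20 | (0.832, 1.000) | (0.338, 0.662) |

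Add one sentence saying that the analysis will use this interval for the group positivity rates and for specificity. The sentence goes beyond correcting the table, but it settles the choice before results are known.

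If Wilson was intended, keep the table, correct the text and caption to say so, round the four truncated limits (0.469, 0.839, 0.055, 0.530), print all limits to three decimals, and name Wilson as the analysis method.

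The cost is one table or one label. With the exact values the stated precision is slightly less favourable. No sample size changes.
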